The clinical experience with PF-06817024 to date has consisted only of data emerging from the current study. As of 01 February, 2018 (the date of the last database cut-off), a total of 71 subjects have received blinded therapy (PF-06817024 or placebo) by IV or SC administration in the current, of which 49 are healthy subjects, 20 are subjects with CRSwNP and 2 are subjects with moderate-severe AD. Escalating doses of PF-06817024 tested in healthy subjects have included single doses of 10 mg, 30 mg, 100 mg, 300 mg and 1000 mg, a repeat dose of 100 mg all administered IV, and a single dose of 30 mg administered SC. Subjects with CRSwNP have been administered a single IV dose of 300 mg of PF-06817024 or placebo. Subjects with moderate-severe AD recruited as of the cut-off date have been administered the first IV dose of 600 mg of PF-06817024 or placebo. Subjects in the healthy and CRSwNP cohorts (Parts 1 and 2) have been followed for up to approximately 1-2 years.

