1.2.5.2. PK Data

Based on a preliminary, draft dataset obtained in January 2018 and including interim data from subjects in the first two parts of the study, a non-compartmental PK analysis was performed and the derived PF-06817024 PK parameters are summarized descriptively in Table 1.

Following single IV doses in healthy subjects, the median time for occurrence of maximal concentration (T_{max}) ranged between 1.76 and 3 hours, while the median T_{max} after SC administration (30 mg) was 338 hours (\approx 14 days). PF-06817024 had a prolonged half-life ($t_{1/2}$) with mean values ranging from 79 to 94 days across all single dose healthy volunteer cohorts. Both maximal plasma concentration (C_{max}) and area under the concentration-time curve from time 0 to infinity (AUC $_{inf}$) appeared to be approximately dose proportional in healthy subjects across the 10-1000 mg IV range (see Table 1), indicating that PF-06817024 exhibits linear kinetics in humans within this dose range. Clearance (CL) values (geometric mean) ranged from 0.00206 L/h to 0.00259 L/h across all single IV dose healthy volunteer cohorts. Using the calculated geometric means of AUC $_{inf}$ after single IV infusion and SC administration of the same dose (30 mg) in healthy subjects (8579/14590, see Table 1), the bioavailability (F) after SC administration is approximately 59% relative to IV infusion.

Multiple dose PK data were available only for 4 healthy subjects from the 100 mg IV cohort who received an additional 100 mg IV dose. The (geometric) mean C_{max} after the second dose was 42.47 µg/mL (geometric CV of 11%) across these 4 subjects and the associated median T_{max} was 1.54 hours. The (geometric) mean area under the concentration-time curve from the time of the second dose until 720 hours post-dose (AUC_{τ}) and until infinity (AUC_{inf}) was 16540 (geometric CV of 13%) and 73400 µg•hr/mL (geometric CV of 23%) respectively. Finally, the mean calculated $t_{1/2}$ after the second dose was 108 days (standard deviation (SD) of 10).

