1.3. Rationale

1.3.1. Study Rationale

1.3.1.1. Parts 1 and 2

This is a first-in-human, placebo-controlled, double blind (pharmacist and sponsor open), single and multiple IV and SC dose study that will be conducted in two parts. Part 1 is a first-in-human, placebo-controlled, double blind, dose escalation study conducted in healthy subjects who may be mildly atopic. In Part 2, single doses of PF-06817024 will be given to one or more cohorts of patients with CRSwNP to enable initial evaluation of safety and tolerability in this patient population.

In all cohorts, the duration of the follow-up is selected to be 7 months after the last dose, which is ≥ 5 times the projected half-life of 41 days. If the emerging data project that half-life is longer than 41 days, the subjects will be asked to return for extended follow-up visit(s) at up to 3 month intervals beyond the last follow-up visit to cover approximately ≥ 5 times the observed half-life

OR of sufficient

duration to have projected exposures decrease below ADA drug tolerance levels CCI

 $^{^{}a}$ $n^{2} = 3$ for subjects remained in the SD period.

[figure not shown]
^b Individual subject values reported.

Part 1 is a first-in-human, placebo-controlled, double blind (pharmacist and sponsor open), dose escalation study in healthy subjects who may be mildly atopic (see Section 3.1 for detailed study overview and Figure 1 for a schematic of the study design). As the current study is the first to dose PF-06817024 to humans, an escalating dose design is proposed with careful assessment and ongoing review of safety and analysis of pharmacokinetics of PF-06817024. The population selected for Part 1 of the study is healthy subjects who may be mildly atopic. For Part 1 Cohorts 1-4, subjects are required to be Phadiatop positive and have an IgE ≥50 kU/L (see Section 4.1 for inclusion/exclusion criteria). ImmunoCAP Phadiatop is a blood test designed to differentiate between atopic and non-atopic subjects. This test demonstrates the presence of specific IgE antibodies to common inhalant allergens. Total IgE levels ≥50 kU/L was selected as a threshold to provide adequate levels of IgE to reliably detect a treatment-related decrease in this pharmacodynamic (PD) biomarker.

UUI

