Figure 1 demonstrates the study design with the select SAD cohorts rolling over into the multiple dose component. Depending on the safety, ^{CCI} and pharmacokinetic data available, dose escalation may be adjusted to doses other than those planned in the study. Intermediate doses can be evaluated instead of or in addition to the planned dose levels. A possible dosing scenario is included in the schematic.

• Cohort 1 (n=8): 10 mg active (n=6) or placebo (n=2), IV.

- Cohort 2 (n=8): 30 mg active (n=6) or placebo (n=2), IV.
- Cohort 3 (n=8): 100 mg active (n=6) or placebo (n=2), IV x 2 doses. [n=4 in MAD cohort].
- Cohort 4 (n=8): 300 mg active (n=6) or placebo (n=2), IV x 2 doses. [no MAD].
- Cohort 5 (n=8): 1000 mg active (n=6) or placebo (n=2), IV x 2 doses. [no MAD].
- *Cohort 6 (n=8): 2000 mg active (n=6) or placebo (n=2), IV.* [dose escalation stopped before 2000 mg dose group].
- Cohort 7 (n=8): 100 mg (first dose) followed by 300 mg (second dose) active (n=6) or placebo (n=2), SC. [Second dose not given, 100 mg dose changed to 30 mg].

2.2. Part 2:

One or more cohorts of CRSwNP patients will receive a single dose of PF-06817024. Randomization will occur after safety data from Day 8 and PK data through at least Day 5 of the same or higher dose in Part 1 of the study has been reviewed and deemed safe.

• Cohorts 8 and 9: Subjects in each cohort will be randomized in either a 1:1 or 2:1 (PF-06817024: placebo) ratio, depending on the number of cohorts and the emerging data. Up to approximately 10 active (per dose) and approximately 15 placebo (overall) subjects will be enrolled in Part 2 for a planned total of up to approximately 35 subjects.

2.3. Part 3

- Part 3 will consist of a single cohort of subjects with moderate to severe AD
- Cohort 13: Approximately 20 subjects in this cohort will be randomized to receive PF-06817024 or placebo in a 3:1 ratio (PF-06817024: placebo). Additional subjects up to a total of approximately 32 [28 actually enrolled] may be enrolled in a 3: 1 ratio (PF-06817024: placebo) CCI Subjects in this cohort randomized to PF-06817024 will receive a planned dosing regimen consisting of a 600 mg IV loading dose followed by 3 doses of 300 mg IV every 4 weeks.

Note that subjects were randomized 2:1 by site under protocol amendment 4 and then randomized centrally in a 3:1 ratio under amendment 5.

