8. STATISTICAL METHODOLOGY AND STATISTICAL ANALYSES

8.1. Statistical Methods

As this is an exploratory study, no formal hypothesis testing will be performed. CCI

Statistical Analyses

All efficacy data from parts 1, 2 and 3will be listed and summarized separately. Safety data will also be summarized combining all three parts as well as separately. Percentages will be presented to one decimal place in all summaries. Minimum and maximum values will be presented to the same number of decimal places as collected on the CRF or with the laboratory screening panel; mean and median will be presented to one further decimal place; standard deviations will be presented to two further places.

In data presentations, results will be sorted by increasing dose level and by study part (SAD/MAD, Nasal Polyps, or Atopic Dermatitis) as appropriate.

Binary variables will be summarized by the number of responders and the number of subjects with data. Percentages will be presented for both observed cases (number of subjects with data at the time point for the denominator) and by non-response imputation (NRI) (number of subjects with data at baseline in the denominator).

Pharmacokinetic Analysis

To assess the pharmacokinetics of PF-06817024, the PK parameters detailed in Section 6.3 will be listed and summarized for subjects in the PK analysis set (as defined in Section 5.2.2). Missing values will be handled as detailed in Section 7. Each PK parameter will be summarized by cohort and will include the set of summary statistics as specified in the table below:

Type of Dosing	Parameter	Summary Statistics
Single Dose [†]	AUC _{last} , AUCinf, AUCinf (dn), C _{max} ,	N, arithmetic mean, median, cv%,
	Cmax(dn), CL, Vss, CL/F, Vz/F	standard deviation, minimum,
		maximum, geometric mean and
		geometric cv%.
	T _{max}	N, median, minimum, maximum.
	t _{1/2}	N, arithmetic mean, median, cv%,
		standard deviation, minimum,
		maximum.
Multiple Dose‡	AUC _{tau} , AUCtau (dn), C _{av} , C _{max} ,	N, arithmetic mean, median, cv%,
	C _{max} (dn), Cmin, Rac AUCtau, Rac	standard deviation, minimum,
	C _{max}	maximum, geometric mean and
		geometric cv%.
	T _{max}	N, median, minimum, maximum.
	t _{1/2}	N, arithmetic mean, median, cv%,
		standard deviation, minimum,
		maximum.

Table 2. PK Parameters to be Summarized Des	scriptively
---	-------------

 \dagger = single dose subjects in Part 1 and all subjects in Part 2, \ddagger = multiple dose subjects in Part 1 and all subjects in Part 3.

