- Individual concentration time plots by cohort and dose (on both linear and semi-log scales) against actual time post first dose (there will be separate spaghetti plots for each cohort per scale).
- Individual concentration time plots by subject (on both linear and semi-log scales) against actual time post first dose (there will be separate plots for each subject).

The length of time used for the x-axes of these plots will be decided on review of the data, and will depend on how long the PF-06817024 concentration is quantifiable in the matrix.

For summary statistics, median and mean plots by sampling time, the nominal PK sampling time will be used, for individual subject plots by time, the actual PK sampling time will be used.

NOTE: Cohort 3 in Part 1 had subjects receiving both single and multiple doses. Therefore all listings, PK parameter summaries, concentration-time profile plots and any other PK data summarizations or analyses should separate single and multiple dose subjects from Cohort 3 treating them as two distinct sub-groups.

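### The SAP's Cohort 3 split leaves first-dose Cmax, Cmax(dn) and Tmax at 100 mg IV summarised from 3 subjects instead of 7, although the second dose cannot affect these values

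*SAP*

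**What the plan says.** The note at the end of the pharmacokinetic part of SAP Section 8.1 concerns Cohort 3 (100 mg IV), where some subjects had one dose and others two. Its scope is "all listings, PK parameter summaries, concentration-time profile plots and any other PK data summarizations or analyses", and no parameter is exempt. The instruction for all of these is that they "should separate single and multiple dose subjects from Cohort 3 treating them as two distinct sub-groups".

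The footnotes to SAP Table 1 (Section 6.3) and SAP Table 2 (Section 8.1) define the single-dose panel as "single dose subjects in Part 1 and all subjects in Part 2". That panel contains Cmax, Cmax(dn) and Tmax as well as AUClast, AUCinf, CL, Vss and half-life. The multiple-dose panel also lists Cmax, Cmax(dn) and Tmax, but does not say after which dose. SAP Section 2.1 records "n=4 in MAD cohort" for Cohort 3.

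The protocol handles the same subjects differently in two places:

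- Table 1 (Section 1.2.5.2) gives 7, 7, 3 for 100 mg IV: 7 in the group, 7 contributing to the summary statistics, and 3 with reportable half-life, AUCinf and CL. Footnote a explains that the 3 is "for subjects remained in the SD period".
- Section 2.2.2 lists first-dose Cmax, Tmax, AUCtau, Cav and their dose-normalised forms as secondary endpoints for the multiple-dose cohorts, separately from the last-dose parameters.

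**The concern.** Up to the second dose, all 7 subjects had received the same treatment: one 100 mg infusion. Parameters that need the full washout cannot be estimated as single-dose quantities in someone who is re-dosed, so a split is needed there. The peak after the first infusion is complete weeks before re-dosing, so nothing is gained by splitting it.

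Two things follow. The 100 mg single-dose summary of first-dose Cmax, Cmax(dn) and Tmax uses fewer than half of the available subjects. And the other four subjects' first-dose values have no stated place: the SAP's multiple-dose list names one Cmax and one Tmax without a dose, although the protocol makes the first-dose values endpoints.

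The ambiguity reaches the plot of dose-normalised Cmax against dose for Part 1, where 100 mg is the middle of the five IV doses given (10, 30, 100, 300 and 1000 mg). The SAP does not say which Cmax would represent a re-dosed subject there. The choice matters: geometric mean Cmax was 42.47 µg/mL after the second dose in 4 subjects (protocol Section 1.2.5.2) and 35.44 µg/mL in the single-dose column of protocol Table 1 (7 subjects). The ratio is 42.47 / 35.44 = 1.20. The groups differ, so this is not a within-subject comparison.

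**Working it through.** **Step 1: subject counts.**

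- On active drug at 100 mg IV: 7 (protocol Table 1; the plan was 6).
- Re-dosed: 4. Protocol Section 1.2.5.2 says "Multiple dose PK data were available only for 4 healthy subjects from the 100 mg IV cohort who received an additional 100 mg IV dose", and SAP Section 2.1 agrees.
- Remaining single-dose: 7 − 4 = 3, which reproduces the third figure in protocol Table 1.

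Cross-check on the 7, assuming the planned 2 placebo subjects in each of the six healthy-volunteer cohorts dosed: active 6 + 6 + 7 + 6 + 6 + 6 = 37, placebo 6 × 2 = 12, total 49. Protocol Section 1.2.5.1 reports 71 subjects dosed, "of which 49 are healthy subjects". The counts agree.

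**Step 2: can the second dose affect the first-dose peak?**

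- Earliest second dose: 4 weeks after the first (Schedule of Activities Table C, footnote a), which is 28 × 24 = 672 h.
- Tmax at 100 mg IV: median 2.00 h, range 1.03 to 8.03 h (protocol Table 1).

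The latest observed peak is more than 660 h before the earliest possible re-dose. First-dose Cmax, Cmax(dn) and Tmax are therefore fixed beforehand in all 7 subjects.

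**Step 3: which other quantities are not protected?**

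- AUCinf, AUCinf(dn), AUClast, CL, Vss and half-life depend on concentrations after the re-dosing time. They stay at 3 subjects under any sensible rule.
- The protocol's dosing interval is 720 h (Table 9). A subject re-dosed at 672 h has not completed it, and re-dosing was allowed at any time from 4 to 12 weeks, so exposure up to the second dose would cover unequal periods.
- If concentrations were pooled up to re-dosing, 4 of 7 subjects (57%) would later leave the profile. SAP Section 7.2 suppresses statistics at a time point when more than half of the data are missing, so the later 100 mg profile could be blanked.

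**Step 4: illustration of size.** The geometric CV of Cmax at 100 mg is 12%, from 7 subjects. The documents give none for the 3, so the same value is assumed. The 90% half-width on the log scale is t(0.95, n − 1) × CV / √n:

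- n = 3: 2.920 × 0.12 / √3 = 0.202
- n = 7: 1.943 × 0.12 / √7 = 0.088

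The ratio is 0.202 / 0.088 = 2.3. It comes from √(7/3) = 1.53 in the standard error and 2.920 / 1.943 = 1.50 in the t quantile. For an assumed CV of 8% to 20%, the half-width runs from 0.135 to 0.337 with 3 subjects and from 0.059 to 0.147 with 7; the ratio does not change.

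**The case against.** The strongest reply is that the SAP loses nothing. It separates subjects and does not exclude them. Concentrations are listed, summarised and plotted by time from the first dose, with a plot for each subject, and first-dose Cmax must be computed for the accumulation ratio. Grouping by subject is a coherent and explicit choice in an exploratory study, protocol Table 1 is only a preliminary summary, and protocol Section 9 lets the SAP modify the outlined methods. No hypotheses are tested, and the planned PK statistics include no confidence interval.

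Most of this stands. A reader might infer that the four subjects' first-dose data are discarded; they are not. A reader might also infer that one missing value would remove 100 mg from the dose-normalised plot. The minimum of 3 evaluable measurements in SAP Section 7.3 governs statistics in summary tables, not individual plotted points, and in the preliminary data all 7 Cmax values were available. Nor does the SAP say that the four subjects leave the plot; they may appear as a second sub-group at 100 mg.

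The reply does not show that the split serves a purpose for the first-dose peak, or where first-dose Cmax and Tmax of re-dosed subjects will be summarised.

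**Conclusion.** The point holds, for first-dose Cmax, Cmax(dn) and Tmax only. The Cohort 3 note and the single-dose footnotes together give a 100 mg single-dose summary of 3 subjects where 7 contribute valid values, and the SAP names no first-dose summary for the other four. Protocol Table 1 already splits by parameter, with 7 for Cmax and Tmax and 3 for AUCinf, CL and half-life.

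The counts rest on the January 2018 preliminary dataset; the SAP's own figure of 4 re-dosed subjects agrees with it. The half-widths of 0.20 and 0.09 show the scale of the lost precision and nothing more: they assume that the 12% CV holds in the 3 subjects, and no PK interval is planned.

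It might seem that the same argument extends to pre-second-dose exposure and concentrations. It does not, because of the unequal intervals, the 720 h dosing interval and the rule on missing data described above. The consequence is a less precise and less clearly defined 100 mg Cmax in a descriptive comparison across doses. No primary endpoint or decision rule is affected.

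**What to change.** Amend the Cohort 3 note in SAP Section 8.1 so that first-dose Cmax, Cmax(dn) and Tmax from all subjects given active drug at 100 mg IV enter the single-dose summary, and so that first-dose Cmax(dn) from the same subjects is used in the dose-normalised Cmax plot. Footnote n by parameter, as protocol Table 1 does. Keep the split for AUClast, AUCinf, AUCinf(dn), CL, Vss, half-life, and the concentration-time summaries and plots.

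The cost is about one sentence and a table footnote, with no new data. There is a small downside: n will differ between rows of the same table, and the four subjects' first-dose values will appear in the single-dose summary while also feeding the accumulation ratios in the multiple-dose sub-group. The footnote should say so.

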8.1.1. Immunogenicity Analysis

Immunogenicity analysis will be conducted on the immunogenicity analysis set as defined in Section 5.5.

ADA and NAb results will be listed and summarized by cohort and time post first dose for samples collected. ADA listing will include ADA testing results and the titer for positive ADA samples. In addition, the PF-06817024 concentration at the matching time point may also be included in the listing to help the interpretation of the ADA results.

An ADA immune response following study drug administration for each subject is defined as:

- A confirmed post-treatment positive ADA result in combination with a negative baseline ADA result; or
- A confirmed post-treatment positive ADA result in combination with at least one dilution factor increase in titer relative to a positive baseline ADA result.

The number of ADA and NAb positive samples will be summarized by cohort and nominal time post-dose. The number of subjects with negative or positive ADA immune response and NAb response will be summarized by cohort in tabular format.

CCI	l	

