Part 3 is a placebo-controlled, double blind, pharmacist and sponsor open, cohort to evaluate safety, tolerability, PK, immunogenicity, of repeat doses of PF-06817024 administered to subjects with moderate to severe AD. Approximately 20 subjects are planned to be enrolled in this cohort. Subjects will be randomized to receive PF-06817024 or placebo in a 3: 1 ratio (PF-06817024: placebo). Additional subjects up to a total of approximately 32 may be enrolled in a 3: 1 ratio (PF-06817024: placebo).

Subjects randomized to PF-06817024 will receive a loading dose of 600 mg IV on Day 1, followed by 3 doses of 300 mg IV every 4 weeks (last dose being on Week 12). Placebo subjects will receive 4 IV doses of matching placebo every 4 weeks. This dosing regimen is expected to decrease the time to steady state

exposure and provide nearly complete target coverage based on currently available in vitro and clinical data.

1.3.1.3. Parts 1, 2, and 3

The duration of the follow-up is selected to be at least 1 year after the last dose of study drug (at Week 12 for Part 3), which is ≥ 3 times the preliminary estimated half-life of approximately 90 days and > 80% exposure (AUC) based on emerging data for the earlier cohorts of healthy subjects, which is adequate to estimate the elimination half-life. If the emerging data project that pharmacologically relevant exposure will extend significantly longer than 1 year, the subjects will be asked to return for extended follow-up visit(s) at up to 3 month intervals beyond the last planned regular visit until one of the following criteria has been met:

• The follow up period from the last dose of study drug is approximately ≥5 times the observed half-life; OR

• The period since the last dose of study drug is of sufficient duration to have projected exposures decrease below ADA drug tolerance levels; OR

The Sponsor will inform the sites when subjects may be discharged from the study based on review of emerging data indicating that one or more of the above criteria are met. Current guidance is that subjects will be in the study for 5 half-lives ie, about 450 days from the last dose.

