2.2.2. Secondary Endpoints

[figure not shown]
Parts 1 and 2

- PK parameters derived from serum PF-06817024 concentrations after single dose or multiple doses of PF-06817024, through the end of the study as data permits:
- Cohorts receiving single dose (IV infusions and SC doses): C_{max} , dose normalized $C_{max}(C_{max}(dn))$, time to reach maximum concentration (T_{max}) , area under the concentration-time profile from time zero to infinity (AUC_{inf}), area under the concentration-time profile from time zero to the time of the last quantifiable concentration (AUC_{last}), area under the concentration-time curve within dosing interval (AUC_{tau}), AUC_{tau}(dn), C_{av} , $t_{1/2}$, mean residence time (MRT), apparent volume of distribution (Vz/F) (SC only), apparent clearance (CL/F) (SC only), V_{ss} (IV only), and clearance (CL) (IV only).

- Cohorts receiving multiple doses (Part 1 only):
 - First Dose: C_{max}, T_{max}, AUC_{tau}, C_{av}, C_{max}(dn) and AUC_{tau}(dn).
 - Last (ie, second) Dose: C_{max} , C_{max} (dn), T_{max} , AUC_{tau} , AUC_{tau} (dn), C_{av} , $t_{1/2}$, MRT, Vz/F (SC only), V_{ss} (IV only), CL/F (SC only), CL (IV only), C_{min} , observed accumulation ratio for C_{max} ($R_{ac}(C_{max})$), and $R_{ac}(AUC_{tau})$.
- Incidence of ADA immune response through the end of the study.

- PF-06817024 plasma concentrations in subjects with moderate to severe AD.
- Incidence of development of anti-drug antibodies (ADAs) and neutralizing antibodies (NAbs) in subjects with moderate to severe AD.

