5.5. Immunogenicity Analysis Set

The immunogenicity analysis set is defined as all enrolled subjects who receive at least 1 dose of investigational product and have at least 1 post-treatment measurement of immunogenicity parameters of interest (ie, ADA [anti-PF-06817024 antibody] or NAb [Neutralizing anti-PF-06817024 antibody]).

CCI

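### The SAP's two-category ADA summary sets no drug-tolerance condition, so subjects sampled only at high drug levels would be tabulated as ADA-negative

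*SAP*

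**What the plan says.** **Classification.** SAP 8.1.1 gives two routes to a positive ADA immune response. One is a confirmed positive after a negative baseline. The other reads: "A confirmed post-treatment positive ADA result in combination with at least one dilution factor increase in titer relative to a positive baseline ADA result". Neither refers to drug concentration. The subject-level table is then: "The number of subjects with negative or positive ADA immune response and NAb response will be summarized by cohort in tabular format". The SAP does not define a negative response separately.

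**Role of drug level.** The same section says "the PF-06817024 concentration at the matching time point may also be included in the listing to help the interpretation of the ADA results". That is optional and does not enter the classification.

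**Denominator.** SAP 5.5 admits treated subjects who "have at least 1 post-treatment measurement of immunogenicity parameters of interest". One sample is enough, whatever the drug level when it was drawn.

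**Endpoint.** Protocol 2.2.2 lists for Parts 1 and 2: "Incidence of ADA immune response through the end of the study". For Part 3 it lists the incidence of ADA and NAb development.

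**Interference is recognised.** Protocol 1.3.1.3 includes among its criteria for ending extended follow-up: "The period since the last dose of study drug is of sufficient duration to have projected exposures decrease below ADA drug tolerance levels". The criteria are alternatives, and meeting any one of them allows discharge. Current guidance there is five half-lives, about 450 days from the last dose.

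**The concern.** When circulating drug exceeds what the ADA assay tolerates, a negative result does not show that antibody is absent. The protocol uses this fact in planning follow-up, but the visible SAP rule does not carry it into the classification. With only two categories, the natural reading is that a subject with no positive sample is counted as negative even if every sample was drawn above tolerance.

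Any such error lowers the reported incidence. Because masking increases with exposure, it could also distort comparisons across doses. The effect carries forward. Under SAP 6.5 only confirmed ADA-positive samples and their baselines go to the NAb assay, so a masked positive is never tested for neutralising activity. If the effect of ADA on safety or PK is assessed (Protocol 9.6), masked positives would sit in the comparison group.

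**Working it through.** **1. The plan's follow-up figure.** 5 × 90 days = 450 days, as Protocol 1.3.1.3 states. The last Part 3 dose is on Day 85, so this is Day 85 + 450 = Day 535. One year after the last dose is Day 450. The last scheduled visit, Day 337, is 252 days after the last dose, or 252/90 = 2.8 half-lives.

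**2. Model inputs.**
- CL = 0.002375 L/h × 24 = 0.057 L/day (Protocol Table 1, 1000 mg IV).
- Q = 0.39 L/day. This comes from the allometric projection in Protocol 1.2.3, not from Table 1.
- V1 = 3.05 L, an assumed value. 1/3.05 = 0.328 µg/mL per mg lies within Table 1's 0.3132 to 0.3544 for 100 to 1000 mg IV.
- V2 = 4.01 L, solved to give a 90-day terminal half-life.
- Regimen: 600 mg on Day 1, then 300 mg on Days 29, 57 and 85.

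**3. Formula.** For each dose D given at time s, C(t) = D[A·exp(−α(t−s)) + B·exp(−β(t−s))], summed over doses. Day d is t = d − 1. α + β = k10 + k12 + k21 = 0.0187 + 0.1279 + 0.0973 and αβ = k10·k21, giving α = 0.2362 and β = 0.00770 per day. A = (α − k21)/[(α − β)V1] = 0.199 and B = (k21 − β)/[(α − β)V1] = 0.1286.

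**4. Check against the plan.** The modelled average concentration is 87.5 µg/mL in the first dosing interval and 130.6 in the last. Protocol 1.3.2.3 predicts 84.1 and 132.5.

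**5. Part 3 levels at ADA sampling times.** Example for Day 337 (t = 336; the fast term is negligible): 600 × 0.1286 × 0.0752 + 300 × 0.1286 × (0.0933 + 0.1157 + 0.1436) = 5.8 + 13.6 = 19.4 µg/mL. Levels before then are about 96, 62, 81 and 97 on Days 8, 29, 57 and 85.

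The table takes a subject with no positive sample and shows the status under a rule that requires the last sample to be at or below tolerance. The tolerances of 100, 50 and 10 µg/mL are illustrative.

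| Last ADA sample | Drug, µg/mL (90 d) | Range, 79–105 d | Tolerance 100 | 50 | 10 |
|---|---|---|---|---|---|
| Day 113 | 109 | 100–116 | inconclusive | inconclusive | inconclusive |
| Day 253 | 37 | 34–40 | negative | negative | inconclusive |
| Day 337 | 19 | 16–23 | negative | negative | inconclusive |
| Day 450 | 8.1 | 6.0–10.8 | negative | negative | negative |
| Day 535 | 4.2 | 2.9–6.2 | negative | negative | negative |

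Status uses the 90-day column. Half-lives of 79 to 105 days span the healthy-cohort means (79 to 94) and the single CRSwNP value in Table 1 (105).

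A one-compartment check with CL 0.00206 to 0.00259 L/h and the same half-lives gives 97–140 at Day 113, 32–49 at Day 253, 16–28 at Day 337 and 2.7–7.5 at Day 535.

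**6. Part 1.** After 1000 mg IV, Day 211 gives 1000 × 0.1286 × exp(−0.00770 × 210) = 25.5 µg/mL. After 10 mg it is 0.26. The 1000 mg level falls to 7.7 at Day 366 and 4.0 at Day 451.

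**7. Effect on incidence, illustration only.** Let p be the proportion positive and f the proportion inconclusive. Incidence among evaluable subjects is p/(1 − f), and the upper bound is p + f. Assume 20 active Part 3 subjects among the 28 enrolled, with 2 positive and 4 inconclusive. Then 2/20 = 10.0% as tabulated, 2/16 = 12.5% among evaluable subjects, and at most 6/20 = 30%. The documents do not give f.

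**The case against.** The strongest reply is that the design already provides late samples. A reader who stops at Day 337 might infer that, at a tolerance of 10 µg/mL, every Part 3 post-dose sample is uninterpretable and most of the cohort unclassifiable. The documents do not support that. ADA is also sampled at extended follow-up and at any end-of-study visit (Protocol 6.2.5, 6.2.7). At all three illustrative tolerances, a completer sampled about 450 days after the last dose with no positive result is still negative under a tolerance-based rule. In Parts 1 and 2, observed half-lives exceed the 41-day trigger for extended follow-up, and Protocol 1.2.5.1 reports follow-up of up to about 1 to 2 years. This part of the reply stands and narrows the point considerably.

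It does not remove the point. The tolerance criterion is one alternative among several and rests on projected, not measured, exposure. Part 3 discharge may be by phone (Protocol 6.2.7), so a final low-drug sample is not assured. Early withdrawals are sampled while drug is high. Protocol 6.1.2.6 still discharges Part 1 single-dose and Part 2 subjects at about Day 211, which conflicts with 1.3.1.3.

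A reader might also infer that the preliminary rate of about 10% with no apparent dose dependency (Protocol 1.2.5.2) is a product of masking. Nothing shows this; a truly low rate fits equally well.

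Two further cautions hold. That non-positive means negative is inferred from the two-category table. Redacted text adjoins both the tolerance wording and SAP 8.1.1, so a rule could exist that is not visible. Finally, SAP 8.1 does require a listing of all concentrations, so a reader could match them by hand, but the incidence table would be unchanged.

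**Conclusion.** The concern holds in limited form. The visible SAP rule has no drug-level condition, so subjects whose only post-dose samples were above tolerance would be tabulated as negative, and ADA incidence can be understated. Those at risk are mainly early withdrawals and subjects without a late follow-up or end-of-study sample. A Part 3 subject leaving just after Day 113 would have every post-dose sample at about 60 µg/mL or more. Subjects sampled to about 450 days after the last dose are affected only if tolerance is below about 3 to 6 µg/mL.

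The direction is supported but the size is not. With the tolerance limit unavailable, the number affected is unknown and may be zero. The levels assume linear PK, similar PK in atopic dermatitis and healthy subjects, and a partly projected model. The study is descriptive with no hypothesis tests, so this is a reporting improvement worth making and does not threaten a decision rule.

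**What to change.** In SAP 8.1.1:
- State the validated drug tolerance of the ADA assay.
- Call a subject ADA-negative only if there is no positive response and the last evaluable post-dose sample has a matched PF-06817024 concentration at or below that limit. Call any other subject without a positive response inconclusive.
- Tabulate positive, negative and inconclusive by cohort, with incidence over all subjects and over evaluable subjects (positive plus negative).
- Make the matched concentration a required column of the ADA listing.

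Separately, Protocol 1.3.1.3 and 6.1.2.6 must be reconciled on the timing of discharge, because this determines whether a late sample exists.

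The cost is SAP wording and one extra table row. At the late Part 3 visits PK and ADA samples are already drawn together (Protocol 6.2.4, 6.2.5, 6.2.7). The drawback is that fewer subjects can be called negative. If tolerance proves high, the inconclusive row is empty and the negative calls are shown to be sound.
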